Limiting intestinal endotoxin translocation is an antiinflammatory strategy. Metabolic endotoxemia is defined by 2-3 times higher circulating endotoxin compared with healthy individuals, but is significantly less than that of levels observed in sepsis patients. Endotoxin is a component of Gramnegative bacteria.² Considerable evidence supports the premise that hepatic NFkB activation is mediated, at least in part, by the translocation of gut-derived endotoxin (e.g. LPS) to the portal circulation, and its ligation to hepatic Toll-like receptor 4 (TLR4). Indeed, nonalcoholic steatohepatitis (NASH) has well-recognized etiology mediated along the gut-liver axis.³ In particular, dietary patterns (e.g. HF diet) that provoke insulin resistance prevent the lowering of intestinal pH otherwise resulting from bacterial fermentation of carbohydrates.⁴ Consequently, the more neutral pH of the gut lumen favors the pathogenic bacteria overgrowth and inhibits the growth of beneficial bacteria (e.g. butvrogenic Bifidobacterium). Short chain fatty acids (SCFAs), especially butyrate, that are synthesized by resident microbes in the gut enhance barrier function.⁵ Indeed, butyrate-producing Clostridium butyricum mitigates NASH in rats (including NFκB p65 expression). These changes correlated with increased expression of intestinal tight junction proteins (TJPs), specifically zonula occluden (ZO) and occludin (OCC), and lowered circulating endotoxin. Thus, treating gut dysbiosis limits barrier permeability, and reduces hepatic exposure to gut-derived, and inflammation-inducing, bacterial products (i.e. LPS).³ This is consistent with NASH patients having intestinal bacteria overgrowth that correlates with circulating endotoxin and expression of hepatic TLR4, but not TLR2.7 Further, our evidence⁸ and that of others⁹ show that mice lacking TLR4/MyD88 signaling are protected from NASH despite increased portal vein endotoxin levels. Antibiotics also attenuate steatosis and endotoxemia in rodents, ¹⁰ and probiotics in obese mice lower NFκB inflammation. ¹¹

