In conclusion, evidence shows that 1) limiting gut-derived endotoxin is an antiinflammatory strategy, 2) GTE lowers TLR4/NFκB-dependent inflammation, and 3) GTE improves gut health through improving gut barrier function and alleviating gut dysbiosis. Our team has the expertise and experience to safely perform controlled crossover interventions to assess metabolic parameters, gut barrier

permeability, and gut microbiota composition. Thus, after completing these studies we expect to substantially advance a critically needed strategy to manage disease-promoting, systemic inflammatory responses that are driven by endotoxemia.

Anticipated Results

Preclinical evidence supports the gut-level benefits of catechin-rich GTE to limit metabolic endotoxemia. ^{8,19} We expect these preclinical findings to be translated to similar gut-level improvements in MetS persons utilizing a novel, catechin-rich GTE confection (i.e. snack food). We expect to achieve >95% compliance (based on returned confections and circulating catechins) without any adverse effects or changes in body mass or energy intakes. Based on our mouse studies, ^{8,19} GTE is expected to decrease serum endotoxin in a time-dependent manner, and most substantially among MetS persons due to their endotoxemia. These benefits are expected to occur through an antiinflammatory mechanism that attenuates gut-derived endotoxin translocation. This would be consistent with GTE reducing endotoxin translocation to the portal vein by increasing intestinal expression of TJPs^{8,19} Thus, GTE will decrease small intestinal and colonic permeability, based on decreased urinary excretion of lactulose/mannitol (0-5 h) and sucralose (0-24 h), respectively. ⁴⁶

Similar to our studies, GTE also will alleviate gut dysbiosis that is known to occur in MetS persons (e.g. depleted populations of SCFA-producing bacteria⁴⁷). Selective antimicrobial activities of GTE will decrease LPS-derived Gram-negative bacteria (e.g. *Bacteroides*).^{42,44} GTE will also increase commensal bacteria, including *Clostridia* (Cluster XIV and IV) and other members of the Grampositive Phyla *Firmicutes* that generate SCFAs.^{48,49} This will be corroborated by greater fecal butyrate and other straight chain SCFAs. Thus, these findings would suggest a mechanism, at least in part, that the alleviation of gut dysbiosis restores butyrate generation.

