Power Calculation and Data Analysis. We performed a power analysis using serum endotoxin (day 28) as the primary outcome. Mean serum endotoxin of MetS and healthy adults was used to predict a conservative 30% improvement by GTE in MetS persons; this corresponds to a 10 EU/mL decrease in endotoxin in MetS. Simulations were used to estimate power based on 20 healthy and 20 MetS adults randomized to treatment vs control in a 50/50 ratio, respectively. Based on a linear model with treatment and health status, and within-subject measures, we will have >90% power (α =0.05) to detect the primary contrast of interest (GTE vs placebo in MetS adults) and additionally, >85% power (α =0.05) to detect an interaction between treatment and health status. Most data will be analyzed by linear mixed effects models (LMMs) with random effect for subjects (to account for repeated measures) and fixed effects for health status, gender, GTE treatment, time period, and their interactions. Multivariate regression analysis will define correlations between study variables with consideration of potential covariates. Statistical significance for all analyses will be set at P≤0.05.

C. Measurement/Instrumentation

Anthropometric Parameters and Blood Pressure. At screening, participants will rest for 15 minutes prior to determining blood pressure using an automated cuff. BMI will be calculated from height determined from a wall-mounted stadiometer and weight from a calibrated scale. Waist circumference will be assessed at the level of the umbilicus using a nonflexible measuring tape.

Blood Chemistries. At screening, fasting plasma glucose, triglyceride, and HDL-cholesterol will be measured by spectrophotometry utilizing validated clinical assays (Pointe Scientific). At day 0, 14, and 28 of the interventions, collected blood will be sent to The Ohio State University Medical Center for metabolic evaluations by assessing a serum chemistry panel [e.g. [e.g. liver function (aminotransferases), renal function (creatinine, BUN), CBC, glucose, insulin, insulin resistance⁷⁹].

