
In the event that a participant is telephoned and is unavailable, a message will be left requesting a callback at a convenient time or that at a member of the study team will try calling again at a later time. No confidential or sensitive information will be shared with third parties or left on answering machines.

Intervention Timeline. Each participant will complete a 2-phase (GTE vs placebo) randomized, crossover study. Each study intervention will consist of 3 study visits (Day 0, 14, 28) over a 4-wk period. After completing the first intervention, participants will undergo a wash-out period (1 month), and afterwards, begin the alternative intervention.

On Day 0, participants will come to the study center in a fasted state and provide a blood sample (45 mL) to measure endotoxin, TMAO, LBP, sCD14, a panel of clinical chemistries, and catechins. Following the blood collection, participants will be instructed on how to complete a 3-d diet record as well as be informed about maintaining a low-polyphenol diet throughout the duration of the intervention. Participants will then be provided a 2-wk supply of confections, for which they will be instructed to consume 6 confections each day (2 confections/meal; 1 g GTE/d).

On Day 14, participants will return to the study center in the fasted state and return any uneaten confections. Another blood sample (45 mL) will be collected for measurement of biomarkers as described above. Participants will then be asked to complete another 3-d diet record and be reminded to keep maintaining a low-polyphenol diet.

Prior to the final visit on Day 28, participants will collect a stool sample during the preceding 3 days. Participants will collect their stool samples in the comfort of their home and will be asked to return the samples on ice or meet with study personnel to return the samples to the study center within 24 h upon

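### A single residual variance across MetS and healthy adults could make the primary MetS test anticonservative; separate variances remove the risk, and the interaction power should be checked against its inputs

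*Combined protocol and SAP*

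**What the plan says.** The paragraph on power and analysis in III.B says: "We performed a power analysis using serum endotoxin (day 28) as the primary outcome". The effect is a 30% improvement in MetS, and "this corresponds to a 10 EU/mL decrease in endotoxin in MetS". The simulations use 20 healthy and 20 MetS adults, "randomized to treatment vs control in a 50/50 ratio, respectively". III.D (Intervention Timeline) makes clear that each person receives both treatments: "Each participant will complete a 2-phase (GTE vs placebo) randomized, crossover study".

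Two powers are stated at α = 0.05: above 90% for the primary contrast (extract against placebo in MetS), and above 85% "to detect an interaction between treatment and health status". No SD, within-subject correlation, healthy-group mean or response, or variance structure is given.

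On analysis, "Most data will be analyzed by linear mixed effects models (LMMs) with random effect for subjects", with fixed effects for health status, gender, treatment, period and their interactions. Group-specific residual variance is neither specified nor excluded.

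Two background statements bear on this. II. Background and Rationale says: "Metabolic endotoxemia is defined by 2-3 times higher circulating endotoxin compared with healthy individuals". Anticipated Results expects endotoxin to fall "most substantially among MetS persons due to their endotoxemia".

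**The concern.** The primary contrast concerns MetS adults only, but the model is fitted to both groups. With one residual variance, the standard error of that contrast comes from the average of the two groups' variances. Biomarkers with a higher mean often vary more, and the plan's own background separates the groups two- to threefold. If healthy adults vary less, they pull the pooled variance down and the MetS test rejects too often. The trial's main claim rests on that test.

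The interaction power raises a second, smaller question. That contrast carries the variance of both groups, and any fall in healthy adults shrinks it. A power only slightly below the primary one is therefore not what equal variances would ordinarily give. The interaction is what would support a claim that the extract works mainly in MetS, and a null result would be read as adequately powered.

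**Working it through.** **Inputs from the documents.** 20 per group, crossover, a 10 EU/mL fall in MetS equal to 30%, α = 0.05, and a 2-3-fold ratio of endotoxin levels. The implied MetS mean is 10/0.30 = 33.3 EU/mL.

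**Assumptions.** Two-sided tests; day-28 within-person differences between treatments (the subject effect cancels); no dropout. SD below means the SD of these differences. The plan's powers cannot be reproduced directly because no SD is given, so I worked backwards.

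**1. Primary test with one residual variance**

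Let r be the healthy SD divided by the MetS SD, s. With equal group sizes the pooled variance averages s²(1 + r²)/2, whereas the MetS contrast needs s². The standard error is therefore multiplied by about √((1 + r²)/2).

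| r | SE factor | Pooled variance, 38 df: type I error | MetS variance only, 19 df |
|---|---|---|---|
| 1 | 1.00 | 5.0% | 5.0% |
| 1/2 | √(1.25/2) = 0.79 | 12.0% | 5.0% |
| 1/3 | √(1.111/2) = 0.75 | 14.4% | 5.0% |

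The error rates come from simulation (200,000 runs, confirmed with a larger run). The values r = 1/2 and 1/3 follow from the 2-3-fold ratio only if SD is proportional to the mean.

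The interaction is largely spared. Its variance is (s² + r²s²)/20, which equals twice the pooled variance over 20, so with equal group sizes pooling gives the right size on average.

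**2. Cost of separate variances if they are equal**

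The SD giving 90% power with 38 df is 13.4 EU/mL. At that SD, a test on the MetS variance alone with 19 df has 88% power.

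**3. The two stated powers under a common variance**

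- Primary noncentrality: 10/(s/√20).
- Interaction noncentrality: (10 − h)/(s√(2/20)), where h is the fall in healthy adults. The standard error is √2 = 1.41 times the primary one.
- If primary power is exactly 90%, s is 13.1 (19 df) or 13.4 (38 df). With h = 0, interaction power is 65% or 63%.

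Conversely, the largest SD that keeps interaction power at 85% is:

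| Healthy fall h (EU/mL) | Largest SD (EU/mL) | Primary power at that SD |
|---|---|---|
| 0 | 10.3 | 98.5% (19 df), 98.9% (38 df) |
| 3.3 | 6.9 | >99.9% |
| 5 | 5.1 | >99.9% |

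The values 3.3 and 5 assume the same 30% fall in healthy adults: 0.30 × 33.3/3 = 3.3 and 0.30 × 33.3/2 = 5.0. The protocol gives no figure for this response.

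**The case against.** The strongest reply is that no document reports unequal variances and no document commits to a single residual variance. A single variance is the usual default for a model described this way, but group-specific variances would also fit the description. That stands: the 12-14% is conditional, and a reader should not infer that the plan rules out the better model. It is silent on the point. The 2-3-fold ratio is also a general definition of metabolic endotoxemia, not the planning data, which III.B says were used but does not print.

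On the powers, a reader might infer that the 85% figure holds only if healthy adults do not respond at all. The documents do not support this. Both figures are lower bounds and no SD is given. With one common variance, both bounds hold alongside a healthy fall of 3.3 EU/mL if the SD is at most 6.9, or of 5 EU/mL if it is at most 5.1, and nothing in the documents excludes such SDs.

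A reader might also treat the pair of powers as evidence of a smaller healthy SD. That requires reading the first bound as almost exactly 90%, which the text does not say. Nor would pooling reproduce such a pair: with SDs of 13.1 and 5.0 and no healthy response, a pooled analysis gives about 97% and 87%.

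Finally, the expectation that the fall in MetS is due to endotoxemia is compatible with little or no fall in healthy adults, and the interaction is an additional aim. Both points are fair and limit the weight of the second question.

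**Conclusion.** The main point holds as a conditional risk to the primary test. If SD scales with mean endotoxin, so that the healthy SD is 1/2 to 1/3 of the MetS SD, a single residual variance gives the primary MetS contrast a type I error of about 12-14% instead of 5%. If the variances are equal there is no inflation. The plan leaves the choice open, and the safer option is cheap.

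The stated powers are not shown to be wrong. What can be said is that, with a common variance and no rise in healthy adults, 90% primary power goes with at most 63-65% interaction power, and 85% interaction power goes with at least 98.5% primary power. The interaction figure therefore depends heavily on SDs and a healthy response that the plan does not state, and only the sponsor can check it.

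**What to change.** 1. Specify that the serum endotoxin model has separate residual variances for MetS and healthy adults, so that the primary contrast uses MetS variability. This is one option in the mixed model. The downside is fewer degrees of freedom for the primary contrast: about 2 points of power (90% to 88%) if the variances are in fact equal. No extra participants are needed.

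2. Check the interaction power against the group SDs, within-subject correlation, healthy response and variance structure actually simulated, and state these beside the two powers. If they do not support more than 85%, restate the figure from those inputs. The back-solved percentages above should not be put in its place. The cost is a short addition to the text and possibly a less favourable stated power.

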Diet Assessment/Control. To improve diet homogeneity and limit potential confounding effects of polyphenol intakes on study outcomes, participants will follow a low-polyphenol diet during each study phase, as described by [name]. In brief, participants will receive weekly dietary education under the auspice of a registered dietitian (PI [name]) to omit or limit polyphenol-rich foods. Participants will be instructed to abstain from foods containing >50 mg/serving of total polyphenols and limit those having 10-50 mg/serving of polyphenols to a maximum of 2 servings/d. Foods containing <10 mg/serving will be unrestricted. This results in a decrease of dietary polyphenols by 45% compared to usual intakes (1568 mg/d), and with 95% adherence. Participants will be provided a list of common polyphenol-rich foods to avoid (see List of Polyphenol-Rich Foods attachment) as well as a form to record any consumption of these foods/drinks. Fiber intakes with this dietary approach are also similar to the low intakes of the typical American diet (~15 g/d). Food records (3-d) will be evaluated on three occasions during the intervention using NDSR software and the NCC Flavonoid and Proanthocyanin database will be used to assess energy, nutrient, and flavonoid intakes as we described. Time the support of the polyphenol study.

Metabolic Endotoxemia. Serum endotoxin will be measured using a fluorometric kit from fasting blood samples at day 0, 14, and 28 as we described. Briefly, the fluorometric assay assesses endotoxin-mediated activation of recombinant Factor C and subsequent cleavage of a fluorogenic substrate (PyroGene rFC; Lonza). In our hands, inter- and intra-assay CV is 4.2-6.1%. To facilitate data interpretation, the following complementary markers of metabolic endotoxemia will be measured in plasma collected at day 0, 14, and 28: trimethylamine N-oxide (TMAO), soluble cluster of differentiation 14 (sCD14), and lipopolysaccharide-binding protein (LBP). Trimethylamine N-oxide is produced by certain gut bacteria and is reflective of gut dysbiosis. Soluble CD14 and LBP guide bacterial toxins to immune cells for recognition and are reflective of increased gut barrier permeability.

Trimethylamine N-oxide will be quantified by LC/MS whereas LBP and sCD14 will be quantified by ELISA using commercial kits.

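### The primary contrast lies within MetS adults, but the only model named is a joint MetS-plus-healthy LMM with no stated residual structure; with one common residual variance, the primary test's type I error depends on an SD ratio the documents do not give

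*Combined protocol and SAP*

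**What the plan says.** Everything specific is in section III.B, paragraph Power Calculation and Data Analysis. The primary outcome is day-28 serum endotoxin, with 20 MetS and 20 healthy adults, all crossed over. Power of more than 90% is claimed "to detect the primary contrast of interest (GTE vs placebo in MetS adults"), and more than 85% "to detect an interaction between treatment and health status". The assumed effect is a 30% improvement; "this corresponds to a 10 EU/mL decrease in endotoxin in MetS". Both power claims come from one linear model containing treatment and health status.

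The analysis sentence reads "Most data will be analyzed by linear mixed effects models (LMMs) with random effect for subjects (to account for repeated measures"), with "fixed effects for health status, gender, GTE treatment, time period, and their interactions". Nothing is said about a residual variance by health status, robust standard errors, a transformation, a variance check, a MetS-only analysis or a degrees-of-freedom method. No endotoxin SD is given for either group.

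Two other places bear indirectly on the spread. Section II states that "Metabolic endotoxemia is defined by 2-3 times higher circulating endotoxin compared with healthy individuals". Section III.C (Metabolic Endotoxemia) gives assay precision, in per cent: "In our hands, inter- and intra-assay CV is 4.2-6.1".

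**The concern.** In a crossover, between-person variance cancels from the treatment contrast and within-person variance sets its standard error. A model with a subject random effect and nothing further has one residual variance for everyone. Here the primary question concerns MetS adults alone, yet half of the information on that variance comes from healthy adults. If MetS adults vary more from visit to visit, the primary P value is too small and the 95% interval too narrow. If they vary less, the test is conservative.

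A higher variance in MetS is the more natural expectation, because the protocol expects higher endotoxin in that group (Anticipated Results: "GTE is expected to decrease serum endotoxin in a time-dependent manner, and most substantially among MetS persons due to their endotoxemia"). The direction is still not established. If the choice is left until data are seen, the primary P value would rest on a post hoc decision.

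**Working it through.** **Inputs.** From section III.B: n = 20 per group, effect 10 EU/mL, alpha 0.05 (taken as two-sided). Assumed: k = within-person SD in MetS divided by that in healthy adults, from 0.5 to 3.

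**The plan's power figures.** They cannot be reproduced, because no SD is stated; one can only solve for the SD of the paired GTE-minus-placebo difference.
- 90% primary power on pooled variance (38 df) needs SD = 13.44 EU/mL. The noncentrality is 10/(13.44/√20) = 3.33.
- 85% interaction power, if healthy adults do not change, needs SD = 10.28 EU/mL. Primary power is then 98.9%.
- At 13.44 the interaction power would be only 63%. Under that assumption, 10.28 is therefore the SD that fits both claims.

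**Bias in the standard error.** The true variance of the MetS mean difference is σ_M²/20. The common-variance model uses, on average, (σ_M² + σ_H²)/2 divided by 20. Hence

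model SE / true SE = √((1 + k²)/2) / k.

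For the interaction, the true variance is (σ_M² + σ_H²)/20. The model uses 2 × (σ_M² + σ_H²)/2 / 20, which is the same. Equal group sizes protect that test.

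**Type I error.** Two sequences of 10 per group, period kept, 36 df for the common variance:

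| k | SE ratio | Common variance | MetS-only, 18 df |
|---|---|---|---|
| 0.5 | 1.58 | 0.3% | 5.0% |
| 0.67 | 1.28 | 1.5% | 5.0% |
| 0.8 | 1.13 | 2.8% | 5.0% |
| 1 | 1.00 | 5.0% | 5.0% |
| 1.25 | 0.91 | 7.5% | 5.0% |
| 1.5 | 0.85 | 9.5% | 5.0% |
| 2 | 0.79 | 12.0% | 5.0% |
| 3 | 0.75 | 14.5% | 5.0% |

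Independent runs agree to about 0.1 point. The interaction test stays between 5.0% and about 5.5% over this range. Section III.B does not say which visits enter the LMM. With all three visits per period, the common-variance figures are 5.1%, 12.2% and 14.4% at k = 1, 2 and 3.

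**What the assay alone implies.** Implied MetS mean: 10/0.30 = 33.3 EU/mL. Healthy mean, if the 2-3 fold ratio applied to these groups (an assumption): 11.1 to 16.7. Within-person SD: 10.28/√2 = 7.3 to 13.44/√2 = 9.5. All other variance is taken as equal.
- Upper end, CV 6.1%: assay SD is 2.03 in MetS and 0.68 in healthy adults. Other variance is 7.27² − 2.03² = 48.7, so k = √(52.9/(48.7 + 0.46)) = 1.04.
- Lower end, CV 4.2%, healthy mean 16.7, SD 9.5: k = 1.01.

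Type I error is then 5.1% to 5.4%.

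**Does splitting only the residual variance suffice?** No. With one common subject variance kept, and between-person variance equal to residual variance in healthy adults, the REML results on 18 df were:
- Both SDs doubled in MetS: the MetS residual variance is overestimated by about 40%, and type I error falls to between 2% and 3%.
- Only the between-person SD halved in MetS: type I error is about 6%.

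**Degrees of freedom.** A MetS-specific variance referred to pooled df gives 5.7% to 5.8%; referred to a normal distribution it gives about 6.5%.

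**The case against.** The strongest reply is that this reads a plan into silence. The section is one summary paragraph about most data. It neither states equal variances nor excludes a richer structure, and LMMs can model unequal variances. That stands in part: it would be wrong to say the protocol has chosen a common variance. But the power statement uses the same kind of joint model for the primary contrast, no other analysis is named for it, and the model as written has one residual variance.

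A second reply is that k is unknown and may be close to 1. That stands fully. A reader might infer from the 2-3 fold statement that k is 2 to 3 and the error 12% to 14.5%. The documents do not support this: the figure is a ratio of means, it contrasts metabolic endotoxemia with healthy people rather than the two enrolled groups, and it becomes an SD ratio only under a constant CV. The one proportional error the protocol reports moves the type I error by 0.4 points at most. Assay error is only part of within-person variation, however, so it does not cap k.

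A reader might also infer that k below 1 would cost the trial much power. That does not fit the plan's own claims. If interaction power is 85% and healthy adults do not change, the average SD is fixed at about 10.28. The common-variance SE is then 10.28/√20 = 2.30, and 10/2.30 = 4.35 against a critical value near 2.03. Primary power stays very high. What remains for k below 1 is a conservative test.

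**Conclusion.** The point holds as a cheap improvement. The mechanism is certain: under a common residual variance, the error rate of the MetS contrast depends on k. Its size in this trial is unknown. It is nil at k=1, 7.5% to 14.5% for k from 1.25 to 3, and conservative below 1. These figures rest on a two-sided 5% test, 20 per group, normal errors and an assumed k. The documents neither show that inflation will occur nor refute the claim of more than 90% power, since no SD is given. The interaction test needs no change on this account.

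**What to change.** Add to section III.B, before data are seen, that the primary MetS contrast will be estimated in one of two ways:

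- from a crossover model fitted to MetS adults only, keeping the period term (18 df on day-28 data); or
- from the joint LMM with both the subject variance and the residual variance specific to health status, using Satterthwaite or Kenward-Roger degrees of freedom.

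A group-specific residual with one common subject variance is not enough. The joint model can stay for the interaction. State which visits enter the primary model, and report the SD for each group used in the power simulation.

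This is wording only, with no added participants or assays. The statistical cost arises if the variances are in fact equal:
- At a paired-difference SD of 13.4 EU/mL, power falls from 90.0% to 88.4% (19 df) or 88.2% (18 df, period kept), slightly under the stated figure.
- At SD 10.3, which fits both power claims if healthy adults do not change, it falls from 98.9% to 98.4%.
- With gender and all interactions in the model (32 to 16 df), the falls are from 89.7% to 87.7% and from 98.8% to 98.3%.

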collection. On Day 28, participants will come to the study center in the fasted state. A fasting blood sample (60 mL) will be collected to measure the biomarkers mentioned above along with analysis of white blood cell inflammatory genes. Following blood collection, participants will perform a gut permeability test. Participants will consume a test beverage that contains sucrose (40 g), lactulose (5 g), mannitol (1 g), sucralose (1 g), and erythritol (1 g) dissolved in water (250 mL). After ingestion of the beverage, participants will be instructed to collect their urine from 0-5 and 6-24 hours in the provided containers.

After completing the first intervention, participants will partake in a wash-out period (1 month) and then repeat the same study procedures (i.e. Day 0, Day 14, Day 28), but will receive the alternative confection (i.e. GTE vs placebo). During each study visit, participants will have access to drinking water and use of the restroom as needed. Details about each study visit and associated test trials that will occur is explained below:

Intervention Phase / Test Confections. During the 4-wk intervention, participants will receive a GTE-rich or placebo (no GTE containing) confection. Confections will be low-carbohydrate and low-calorie. Each serving (6 g) provides <8 kcal, while delivering 1 g of decaffeinated GTE. The catechin profile (82% catechins (w/w); 63% EGCG, 18% EGC, 10% ECG, 9% EC) is similar to that of freshly brewed green teas. Sucrose will be the main carbohydrate source because sugar alcohols alter microbiota composition⁸¹ and would confound interpretation. Decaffeinated GTE was chosen to minimize potential side effects such as excess caffeine consumption or caffeine/drug interactions that could result from comorbidity management of metabolic conditions. Placebo confections will be identical to GTE-rich confections, but without GTE. Confections will be packaged in single-serve, oxygen impermeable containers, and coded for study blinding. Participants will be asked to store the confections in the refrigerator to maintain quality and freshness.

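### Day-0 endotoxin is collected in both phases but has no stated role in the day-28 primary model; adjusting for it is a cheap improvement that may add precision

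*Combined protocol and SAP*

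**What the plan says.** All of the analysis text is in Power Calculation and Data Analysis (section III.B). The outcome and its time point are clear: "We performed a power analysis using serum endotoxin (day 28) as the primary outcome". The design effect is "a conservative 30% improvement by GTE in MetS persons; this corresponds to a 10 EU/mL decrease in endotoxin in MetS", with "20 healthy and 20 MetS adults" "randomized to treatment vs control in a 50/50 ratio". The stated power is above 90% for GTE versus placebo in MetS adults and above 85% for treatment by health status. The mixed model is given as a "random effect for subjects (to account for repeated measures) and fixed effects for health status, gender, GTE treatment, time period, and their interactions". Covariates are mentioned only for the separate regressions that examine correlations between study variables.

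The sampling schedule goes further than the model. Metabolic Endotoxemia (III.C) states: "Serum endotoxin will be measured using a fluorometric kit from fasting blood samples at day 0, 14, and 28 as we described". Intervention Timeline (III.D) has participants "repeat the same study procedures (i.e. Day 0, Day 14, Day 28") after the wash-out, on the other confection. Each person therefore has two pre-dose values, one per phase.

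**The concern.** The random subject effect removes a person's constant level. It does not remove how far that person stood above or below that level when a given phase began. If such deviations persist to day 28, the two day-0 values carry information about the primary difference, and the listed model leaves it unused.

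The text also leaves open how day 0 enters. If *time period* means crossover phase and only day 28 is modelled, day 0 is dropped. If it means study day, the day-0 values become responses. An analyst could then report GTE versus placebo at day 28, a GTE-by-day contrast that amounts to change from day 0, or a GTE term averaged over a pre-treatment day. These tests differ in power, and the power statement is made for day 28. At stake is some precision in a 20-person contrast, and a choice of primary test that should be closed before the data are seen.

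**Working it through.** **Inputs.** From III.B: a 10 EU/mL effect, 20 MetS and 20 healthy adults who each cross over, and α = 0.05. Assumed: two-sided test, no dropout, no effect in healthy adults, and equal variance of the within-person differences at day 0 and day 28. The protocol gives neither the SD of endotoxin nor r, so the stated power cannot be reproduced. The SD of the within-person GTE-minus-placebo difference (SDd) has to be back-solved.

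**Back-solving SDd (noncentral t).**
- MetS contrast, SE = SDd/√20, 18 df (period-adjusted). Exactly 90% power needs SDd = 13.04: SE = 13.04/4.472 = 2.92 and 10/2.92 = 3.43. With 19 df the answer is 13.1, and with 36 df it is 13.4.
- Interaction, SE = SDd·√(2/20), 36 df. Exactly 85% power needs SDd = 10.27: SE = 3.25 and 10/3.25 = 3.08.
- Cross-check: SDd 13.0 gives only about 66% interaction power. SDd 10.3 gives about 98% for the MetS contrast (18 df; 98.9% with 36 df). Both stated minimums are met only if SDd is about 10.3 or less, so both values are carried forward.

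**Variance relative to day 28 alone.** Let D0 and D28 be the within-person differences at the two days, each with variance σ².
- Adjusted for day 0: Var(D28 | D0) = σ²(1−r²).
- Change from day 0: Var(D28−D0) = 2σ²(1−r), which exceeds σ² whenever r < 0.5.

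Under a random intercept alone the person's level cancels from both differences, what remains is independent, and r = 0.

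**Power by formula: day 28 alone / adjusted / change.** The MetS column uses 18 df (17 when adjusted).

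| r | 1−r² | 2(1−r) | MetS contrast, SDd 13.0 | Interaction, SDd 10.3 |
|---|---|---|---|---|
| 0 | 1.00 | 2.00 | 90 / 90 / 63% | 85 / 85 / 56% |
| 0.2 | 0.96 | 1.60 | 90 / 91 / 73% | 85 / 86 / 66% |
| 0.3 | 0.91 | 1.40 | 90 / 92 / 78% | 85 / 88 / 72% |
| 0.5 | 0.75 | 1.00 | 90 / 96 / 90% | 85 / 93 / 85% |

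At SDd 10.3, change from day 0 keeps about 83% power for the MetS contrast at r=0 (85% with 36 df).

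**Cost of estimating the slope.** The formula is slightly generous because the slope must be estimated. Simulation with one slope pooled over all 40 people gives these effects of adjustment:
- r=0: a loss of about 1 point.
- r=0.15–0.2: break-even.
- r=0.5: a gain of about 5 points for the MetS contrast at SDd 13.0, about 1 point at SDd 10.3, and about 8 points for the interaction at SDd 10.3.

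Fitting the slope in the 20 MetS adults alone costs up to 2 points at r=0.

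**How day 0 enters.** This was simulated with a random-intercept model in 20 people, SDd 13, and 60% of the variance between persons. At r=0, power was 0.90 for day 28 alone, 0.88 with day 0 split into person mean and phase deviation, and 0.81 with the raw day-0 value as the only baseline term. At r=0.5 the split and raw forms both gave 0.96. The raw form does worse at low r because between-person level contaminates the slope.

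**The case against.** A reader might infer that the trial will be analysed as change from day 0 and will fall to 63% power. The documents do not support that. III.B names day-28 endotoxin and GTE versus placebo in MetS adults. A model holding all three days can deliver that contrast at day 28, and if *time period* means crossover phase there is no GTE-by-day term at all. The 63% also assumes SDd 13.0, which misses the stated interaction power. At SDd 10.3 the day-28 MetS contrast is already near 98%, which leaves adjustment little to add to it.

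A reader might also infer that omitting day 0 necessarily wastes precision. In a crossover that is true only if r is above zero, and the plan's own random-intercept structure implies r=0. The schedule argues against a large r. The four draws (day 0 and day 28 of each phase) fall about four weeks apart, because the wash-out lasts about a month. If deviations decay exponentially (an assumption) with four-week autocorrelation ρ, then r = (ρ−ρ³)/(2(1−ρ²)) = ρ/2. So r=0.3 needs ρ=0.6, and r=0.5 needs ρ close to 1 unless there is an extra phase-specific effect. In addition, III.D places the day-0 draw before the low-polyphenol diet instruction, so the two days may reflect different diets.

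Finally, large gains from adjustment and a much weaker change score need opposite values of r, so both cannot be claimed at once.

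These points stand, and they limit the size of the concern. They do not supply the missing definition of *time period* or a stated role for day 0. With r unknown, the split adjustment risks about 1 point and can gain several.

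**Conclusion.** The specification gap is real: two pre-dose endotoxin values per person are collected, no model term uses them as a baseline, and *time period* is undefined. Adjustment is worth specifying because its downside is small across the plausible range of r. Its benefit is conditional. It is nil or slightly negative below r of about 0.15–0.2, and at r=0.5 it is about 5 points for the MetS contrast at SDd 13.0, about 1 point at SDd 10.3, and about 8 points for the interaction at SDd 10.3. Change from day 0 is weaker than day 28 alone whenever r < 0.5. At r=0 it has about 63% power if day-28 power is exactly 90%, and about 83% at the SD implied by 85% interaction power. That is a reason to exclude it in writing, not evidence that the plan intends it.

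All of these figures rest on back-solved SDs, an assumed r, equal variances at the two days and no dropout. This is a cheap improvement, not a demonstrated loss of the stated power.

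**What to change.** Amend the analysis text in III.B to:

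1. State that the primary contrast is GTE versus placebo at day 28 in MetS adults, and define *time period* as crossover phase or study day.
2. Adjust for day-0 endotoxin, entered as two terms: the person's mean over the two phases, and the phase value's deviation from that mean. For complete pairs this is equivalent to regressing the within-person day-28 difference on the within-person day-0 difference. Use one slope pooled over all 40 participants.
3. Not enter the raw day-0 value as the only baseline term.
4. Not use simple change from day 0, or a GTE term averaged over day 0, as the primary test.

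The cost is wording, one degree of freedom for the within-person slope, and about 1 power point if r is near zero (up to 2 if the slope is fitted in MetS adults alone). No new data are needed.
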